7.5.6 PVR Volume

PVR volume in mL and corresponding change from baseline values will be summarized by treatment group and visit (baseline and Week 12) for continuous values as well as using the following categories:

- ≥ 0 mL to < 150 mL
- ≥ 150 mL to < 300 mL

- ≥ 300 mL

A shift table for changes from baseline to each post-baseline visit for PVR volume based on the 3 categories above will be performed for each treatment group.

7.5.7 Weight, Height, and BMI

A descriptive summary for values of height (baseline only) weight in kg and BMI in kg/m^2 at each post-baseline visit and the changes from baseline will be provided at each visit. A listing will also be provided.

7.5.8 Pregnancies

A listing of pregnancy testing will be provided.

7.6 Analysis of Pharmacokinetics (PK)

Not applicable

7.7 Analysis of PD

Not applicable

7.8 Subgroups of Interest

Primary efficacy endpoints and selected safety variables (treatment emergent adverse events and vital signs) will be summarized by treatment group for the subgroups defined on the basis of the categorized variables listed below:

Grouping variable	Subgroups
Race	White
	Black or African American
	Asian
	American Indian/Alaskan Native
	Hawaiian or Other Pacific Islander
	Other
Age group	< 75 years
	≥ 75 years
Sex	Female
	Male

7.9 Other Analyses

Not applicable

7.10 Handling of Missing Data, Outliers, Visit Windows, and Other Information

7.10.1 Missing Data

Missing primary and secondary efficacy endpoints will be handled by LOCF for continuous variables, and non-responder imputation for binary variables.

For all OAB-q scales and subscales, if <50% of the items are missing, the scale/subscale should be retained with the mean scale score of the items present used to impute a score for the missing items. If >=50% of the items are missing, no scale/subscale score should be calculated, the scale/subscale score should be considered missing.

As a general principle, imputation of missing dates for variables will not be done. Exceptions are for start and stop dates of study drug intake, AEs and concomitant medications. The imputed dates will be used to determine whether the medication was taken prior to or during the double-blind treatment period. Listings of the AEs and concomitant medications will present the actual partial dates; imputed dates will not be shown.

7.10.1.1 Imputation of Study Drug Start Dates and Study Drug End Dates

Imputation of Study Drug Start Dates

Run-In Period

For subjects who are not Screen Failures, the first dose date of placebo run-in will be imputed if both of the following criteria are met:

- There is a missing or partial date for the first dose of placebo run-in study drug AND
- The number of tablets dispensed at the Screening Visit does not equal the number of tablets returned (including missing values).

If both criteria are met, then the first dose date of placebo run-in study drug is defined as the first non-missing date in the following order:

- Dispense date at Screening Visit +1 day
- Date of the Screening Visit +1 day

Double-Blind Treatment Period

For subjects who are randomized to double-blind treatment, the first dose date of double-blind treatment study drug will be imputed if both of the following criteria are met:

- There is a missing or partial date for the first dose of double-blind treatment AND
- The number of tablets dispensed at the Randomization Visit does not equal the number of tablets returned (including missing values) AND
- Dispensed date is non-missing.

If all the above criteria are met, then the first dose date of double-blind treatment is defined as:

Dispense date at the Randomization Visit +1 day

Imputation of Study Drug End Dates

Run-In Period

For subjects who are not Screen Failures, the last dose date of placebo run-in will be imputed if both of the following criteria are met:

1. There is a missing or partial date for the last dose of placebo run-in study drug AND
2. The number of tablets dispensed at the Screening Visit does not equal the number of tablets returned (including missing values).

If both criteria are met, then the last dose date of placebo run-in study drug is defined as the first non-missing date in the following order:

- Date of the day before the first dose of double-blind treatment in the double-blind treatment period,
- Day of the dispense date at the randomization visit
- Day of the randomization visit (Visit 2)
- Date of the first dose of placebo run-in study drug + 1 day
- Dispensed date at the Screening Visit + 1 day
- Date of the Screening Visit + 1 day

Double-Blind Treatment Period

For subjects who are randomized to double-blind treatment, the last dose date of double-blind treatment study drug will be imputed if all the following criteria are met:

- a. There is a missing or partial date for the last dose of double-blind treatment AND
- b. The number of tablets dispensed at the Randomization Visit does not equal the number of tablets returned (including missing values).

If only the day is missing for the last dose date of double-blind treatment, the last day of the month under consideration will be used.

If the month and/or year are missing for the last dose date of double-blind treatment, then the last dose date of double blind treatment is defined as the first non-missing date in the following order:

- Last dispense date of the double-blind period + 1 day

- Date of the first dose of double-blind treatment in the double-blind treatment period + 1 day
- Date of the randomization visit + 1 day.

For imputing the last dose date of placebo run-in study drug and double-blind treatment study drug, an imputed first dose date should not be used but the next imputation rule should be used instead.

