5.2.1 Reasons for Exclusion From PPS

The following criteria listed in Table 3 may lead to subject's exclusion from PPS.

Table 3. Criteria for Assessing Major Protocol Violations which could potentially Impact Efficacy Assessments

Number	MPV Criteria
Treatment Violations	
1	Double Blind treatment duration of less than 53 days
2	No measurement of the primary efficacy endpoint available at or after Visit 2
3	Treatment compliance of less than 70% between randomization and last visit
4	Administration of excluded concomitant treatment as described in the Study Protocol.
Inclusion Criteria Violations	

5	Subject did not experience at least one incontinence episode based on the 3-day micturition diary at baseline.
6	Subject did not experience at least 3 episodes of urgency (grade 3 or 4) based on the 3-day micturition diary at baseline.
7	Subject did not experience an average of greater than or equal to 8 micturitions/day based on the 3-day micturition diary at baseline.
Exclusion Criteria Violations	
8	Subject was non-compliant during 2-week placebo run-in period, defined as taking less than 80% or greater than 120% of study medication
9	Subject did not complete all 3 days of the baseline 3-day micturition diary
10	Unblinding of Study Drug
11	Error in Study Drug Administration
Other Exclusions from PPS	
12	Subject did not complete at least 2 days of the EOT 3-day micturition diary

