6.2 Safety Variables

Safety will be assessed by evaluation of the following variables:

- Treatment-emergent adverse events (TEAEs; frequency, severity, seriousness, and relationship to study drug).
- Adverse Events of Possible Hepatic Origin (See [Appendix 1](#))
- Acute Urinary Retention
- Urinary Tract Infections
- Clinical laboratory variables (hematology, biochemistry including liver function tests, and urinalysis)
- Cardiovascular events, vital signs (systolic and diastolic blood pressure and pulse rate), MI, Stroke and serious arrhythmias.
- Montreal Cognitive Assessment (See [Appendix 5](#))
- Physical Examination
- 12-lead electrocardiogram (ECG)
- Post-Void Residual Volume

TEAE is defined as an adverse event observed after starting administration of the test drug/comparative drug. If the adverse event occurs on Day 1 and the onset check box is marked “Onset after first dose of study drug” or the onset check box is left blank, then the adverse event will be considered treatment emergent. If the adverse event occurs on Day 1 and the onset check box is marked “Onset before first dose of study drug”, then the adverse event will not be considered treatment emergent. If a subject experiences an event both during the pre-investigational period and during the investigational period, the event will be considered as a TEAE only if it has worsened in severity (i.e. it is reported with a new start date). All adverse events collected that begin within 30 days after taking the last dose of study drug will also be counted as TEAEs.

A drug-related TEAE is defined as any TEAE with possible or probable relationship to study treatment as assessed by the investigator or with missing assessment of the causal relationship.

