6.3 Other Variables

6.3.1 Duration of Exposure

For each subject the duration of exposure on double-blind treatment will be calculated in days using the following formula:

$$(Date \text{ of } last \text{ dose } of \text{ study } drug - Date \text{ of } first \text{ dose } of \text{ study } drug) + 1$$

where the dates of the first and last known double-blind treatment are recorded on the study drug dosing eCRF pages. If they are missing, then imputed dates as per Subsection 7.10.1.2 will be used. Any gaps in dosing will be included in the total number of days on double-blind treatment.

The duration of exposure during the placebo run-in will be calculated in a similar way based on the dates of first and last dose of the study drug administration.

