7.10.3.1 Analysis Visit Windows for Efficacy and Safety Variables

All the efficacy and safety assessments for a treatment period will be allocated based on the tables below.

Efficacy:

Analysis visit	Target day	Actual assessment day
Screening	Day -28	-38 to -18
Placebo Run-In	Day -14	-17 to 0
Baseline	Day 1	Day 1 ^a
Week 4	Day 30	15-42
Week 8	Day 60	43-70
Week 12/End of Treatment	Day 90	71-98
Follow Up Phone Call	Day 120	EOT+14

After Placebo Run-In, visit windows/study days will be calculated based on the Baseline (Visit 3) date.

Safety:

Analysis visit	Target day	Actual assessment day
Screening	Day -28	-38 to -18
Placebo Run-In	Day -14	-17 to 0
Baseline	Day 1	Day 1 ^a
Week 4	Day 30	2-45
Week 8	Day 60	46-75
Week 12/End of Treatment	Day 90	76-97
Follow Up Phone Call	Day 120	EOT+14

1. After Placebo Run-In, visit windows/study days will be calculated based on the Baseline (Visit 3) date.

For efficacy variables recorded in the 3-day micturition diary, the following rules will apply:

1. As micturition diary data are to be recorded from midnight 3 days prior to a visit to midnight 1 day prior to a visit, micturition diary records which have the same date as a visit date should be excluded from the analysis. Non-micturition questionnaire assessment dates will be compared to the eDiary dates and used to flag which diary records should be excluded.
2. Any diary days which are > 7 days after the last dose of double-blind treatment will not be included in the analysis.
3. Average values or number of episodes for count data will only be calculated if at least 2 valid diary days are available within the specified window. In the case that only 1 valid diary day is available, then no value will be calculated.
4. If there are more than 3 valid diary days available for a visit, the average will be based on the last 3 days prior to the scheduled visit.
5. Duplicate records (same time and episode characteristics) per day during the 3-day micturition diary period will be excluded.

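### Month-end imputation of a last-dose date with only the day missing has no upper bound, so it can overstate exposure and stretch the rules that depend on last dose

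*SAP*

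**What the plan says.** SAP 7.10.1.1 imputes a missing or partial last double-blind dose date when a tablet-count condition also holds: "The number of tablets dispensed at the Randomization Visit does not equal the number of tablets returned (including missing values"). Almost any treated subject meets that condition. Two rules follow.

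- Day missing, month and year known: "If only the day is missing for the last dose date of double-blind treatment, the last day of the month under consideration" is taken. No check against a visit, a discontinuation date, an eDiary record or a tablet count is attached.
- Month or year missing: the first choice is "Last dispense date of the double-blind period + 1 day", which errs towards a short exposure.

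The last-dose date is then used in several places.

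- **Exposure (SAP 6.3.1):** last dose minus first dose plus 1. The text says "If they are missing, then imputed dates as per Subsection 7.10.1.2 will be used". That subsection concerns adverse event onset; the dosing-date rules are in 7.10.1.1.
- **Per Protocol Set (SAP 5.2.1, Table 3, criterion 1):** "Double Blind treatment duration of less than 53 days".
- **TEAE definition (SAP 6.2):** "All adverse events collected that begin within 30 days after taking the last dose of study drug will also be counted as TEAEs".
- **Diary data (SAP 7.10.3.1, rule 2):** "Any diary days which are > 7 days after the last dose of double-blind treatment will not be included in the analysis".

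**The concern.** Month end is the latest date compatible with the recorded month. Without a bound, the imputed last dose can come after the visit at which treatment ended, and even after the subject has left the study. Every error is in the same direction: the imputed date is never too early.

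The direct consequence is overstated exposure, which can also keep a briefly treated subject from meeting per-protocol criterion 1. The TEAE window and the diary cut-off are measured from the same date, so they move later with it. The diary cut-off matters most in principle, because it governs both co-primary endpoints, but it is reached by the narrowest route.

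Elsewhere the SAP does check imputed dates. Imputed adverse event onset is held to the event's end date (7.10.1.2), imputed medication start to the stop date (7.10.1.3), and imputed OAB onset to the consent date (7.10.1.4).

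**Working it through.** The documents state no figure for how often the day is missing or how many days the rule adds, so there is nothing of the plan's own to reproduce on this point. The checks below are calendar arithmetic. A uniform true day *d* within a month of *M* days is my assumption.

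**1. Size of the overshoot.** Overshoot = *M* − *d*. Its mean is (*M* − 1)/2, and the share above 7 days is (*M* − 8)/*M*.

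| Month length | Maximum | Mean | Share > 7 days |
|---|---|---|---|
| 28 | 27 | 13.5 | 20/28 = 71% |
| 30 | 29 | 14.5 | 22/30 = 73% |
| 31 | 30 | 15.0 | 23/31 = 74% |

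Over all dates in 2015–2016 the mean is 14.7 days and the share above 7 days is 73.7%.

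**2. Exposure in a completer.** First dose 10 July 2015, last dose 1 October (Day 84). The imputed date is 31 October, so exposure reads 84 + 30 = 114 days. A cap at the final visit, if held on 1 October, restores 84.

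**3. Per-protocol criterion 1.** The largest overshoot is 30 days, so a true duration as short as 53 − 30 = 23 days can read as 53 and no longer meet the criterion.

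**4. An early stopper.** First dose 2 January 2015, last dose 2 March (Day 60), diary on 23–25 March (Days 81–83, inside the Week 12 efficacy window of 71–98). The final visit is assumed to be 26 March (Day 84), the day after the last diary day.

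| Last-dose date used | Exposure | Diary cut-off (+7 days) | Diary of 23–25 March |
|---|---|---|---|
| True, 2 March | 60 | 9 March | dropped |
| SAP rule, 31 March | 89 | 7 April | kept |
| Capped at visit, 26 March | 84 | 2 April | kept |
| Discontinuation date, assumed recorded as 3 March | 61 | 10 March | dropped |

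The visit cap removes exposure days after the visit. It does nothing for the diary.

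**5. Why the visit cap cannot help the diary.** SAP 7.10.3.1 rule 1 excludes visit-day records, so the analysed diary days for a visit precede it. A diary day *g* days after the true last dose should be dropped when *g* > 7, but under the month-end rule it is kept when *d* + *g* ≤ *M* + 7. In a 31-day month that is (38 − *g*)/31 of the possible dates: 24/31 = 77% at *g* = 14, 17/31 = 55% at *g* = 21, and 10/31 = 32% at *g* = 28. With the visit cap the shares are identical, because any date capped at the visit already lies after the diary day.

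**6. TEAE window.** Nominally it can reach 30 + 30 = 60 days after the true last dose. Collection ends at the follow-up call, 4 weeks after End of Treatment (Protocol 5.4.4 and 5.4.10). In example 4 the true window ends on 1 April and the imputed one on 30 April. If the call follows the 26 March visit by 28 days, collection stops about 23 April, so about 22 extra days are captured, not 29. For a completer who doses up to Visit 6, the call comes about 28 days after last dose and almost nothing is added.

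**7. Compliance.** SAP 6.3.2 covers subjects whose tablet count and duration of exposure are known. SAP 7.3.2 requires first and last treatment days to be known and provides an Unknown category. SAP 6.3.1 lets imputed dates into exposure. If they did enter, a fully adherent one-tablet subject would read 84/114 = 74% in example 2 and 60/89 = 67% in example 4, against the 70% limit in per-protocol criterion 3. The text does not settle whether they do.

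**The case against.** The strongest reply is that little of this reaches a result that matters.

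- **Consistency.** The like-for-like rule, the medication stop date in SAP 7.10.1.3, also uses month end without a cap. The rules that carry a check are for start or onset dates. A late last dose also widens the TEAE window, which is the cautious direction for safety. This stands as an explanation of the choice, but it does not justify an exposure date after the subject's last visit.
- **Rarity.** The diary effect needs a subject who stopped early, has only the day missing, and has at least 2 valid diary days more than 7 days off drug inside an analysis window. Completers dosing up to Visit 6 are unaffected. Data are reviewed before lock (SAP section 1), and the eDiary records intake times (SAP 6.1.3.1), so some dates may be recovered. This stands.
- **Inference.** The SAP expressly sends imputed dates only to exposure (6.3.1) and to placing medication before or during treatment (7.10.1). Their use in the 7-day and 30-day rules is inferred. That is fair, but for these subjects the imputed date is the only last-dose date the SAP supplies.
- **Per-protocol status.** The Table 3 criteria only may lead to exclusion, final judgement is made before unblinding, and the set also requires completion of the study (SAP 5.2 and 5.2.1). So passing criterion 1 does not by itself put a subject in the set.

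A reader might go further and infer that the missing visit cap is what lets off-drug diaries into the co-primaries. It is not: the diaries precede the visit, and the month-end rule itself is responsible. Nor do the documents support saying that adherent subjects will fail the compliance criterion, since 6.3.2 and 7.3.2 can be read as leaving them out of the calculation.

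**Conclusion.** This is a real but minor specification defect. Followed as written, the rule can date the last dose after the final visit. It overstates exposure by about 15 days on average and 30 at most for each subject with only the day missing, assuming a uniform true day, and it can take a duration as short as 23 days past per-protocol criterion 1. The TEAE window is extended, but observation stops at the follow-up call, so the 60-day figure is nominal.

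The effect on the co-primaries is secondary and rarer. It might be read as a bias in the primary result, but the documents do not show one: they give no rate of missing days and no reason to expect a difference between arms. The expected dropout of at least 15% (SAP section 4) bounds neither, because it does not say how many early stoppers lack only the day or keep a diary off drug. The effect on compliance is unclear rather than demonstrated.

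**What to change.** In SAP 7.10.1.1, when only the day is missing, set the last double-blind dose to the earliest of:

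1. the last day of the recorded month;
2. the End of Treatment or early-discontinuation visit date;
3. the treatment-discontinuation date, where recorded;

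but not earlier than the last eDiary medication-intake record in that month.

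Item 2 removes exposure after the final visit. Only item 3 can correct the diary cut-off. The documents mention discontinuation status and reason (SAP 7.2.1, Protocol 8.1.2) but describe no date field, so the sponsor should confirm that one exists. If it does not, the diary effect remains. The eDiary record is a floor and can only lengthen the imputed exposure.

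At the same time, correct the reference in SAP 6.3.1 from 7.10.1.2 to 7.10.1.1, and state whether imputed dates enter compliance, since 6.3.1 and 7.3.2 point different ways.

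The cost is a short SAP edit and a small programming change, with slightly shorter imputed exposure as the only downside.

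### When the month or year of the last dose is missing, the SAP dates it one day after the last dispensing, which cuts a completer's exposure to about 57 days and can discard the Week 12 diary

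*SAP*

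**What the plan says.** SAP 7.10.1.1 imputes a missing or partial last double-blind dose date if the tablets dispensed at randomization differ from those returned, or if those counts are missing. There are two branches.

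- Day only: "If only the day is missing for the last dose date of double-blind treatment, the last day of the month under consideration will be used".
- Otherwise: "If the month and/or year are missing for the last dose date of double-blind treatment", the date is by definition the first available of three entries. The first is "Last dispense date of the double-blind period + 1 day". The other two are the first double-blind dose plus one day and the randomization visit plus one day.

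The list contains no end-of-treatment visit, drug-return or e-diary date.

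Three other rules use the last dose date.

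- SAP 6.3.1 computes exposure as last minus first dose plus one and expressly uses imputed dates. It cites 7.10.1.2, which covers adverse event onset; the dosing rules are in 7.10.1.1.
- SAP 7.10.3.1: "Any diary days which are > 7 days after the last dose of double-blind treatment will not be included in the analysis".
- SAP 6.2: "All adverse events collected that begin within 30 days after taking the last dose of study drug will also be counted as TEAEs".

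For the start of run-in, the first choice is "Dispense date at Screening Visit +1 day", followed by the Screening date plus one day. The list for the end of run-in labels the randomization visit as Visit 2.

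**The concern.** None of the three entries reflects when treatment stopped. The first allows one day of dosing from the final supply, although that supply covers about four weeks for a subject who stays to Week 12. A completer whose last dose date lacks a month or year would therefore be recorded as stopping at about Week 8.

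For exposure this follows directly from the text. If the same date governs the diary cut-off, an observed on-treatment Week 12 diary is set aside and SAP 7.1 replaces it with the last earlier diary, for both co-primary endpoints. The Week 8 diary is completed before Visit 5, at which a dose increase is still possible, so it is not a neutral substitute. If the date also governs the adverse event window, later events are not counted as treatment-emergent.

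**Working it through.** The plan gives no figure of its own on this point. The check is day arithmetic, with Day 1 as the first double-blind dose.

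**Inputs**
- Last scheduled dispensing: Visit 5, Day 56 ± 7 (protocol Table 1). SAP Table 1 puts Visit 5 at Day 60 ± 7 and also marks dispensing at Visit 6.
- Visit 6: Day 84 ± 7 (protocol) or Day 90 ± 7 (SAP).
- Week 12 diary: the three days before Visit 6 (protocol 5.3.1).
- At least two valid diary days are required (SAP 7.10.3.1).
- PPS criterion 1: double-blind treatment shorter than 53 days (SAP Table 3).

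**Formulas**, where V5 is the day of Visit 5:
- imputed last dose = V5 + 1, which is also the exposure in days
- last usable diary day = V5 + 1 + 7
- end of treatment-emergent window = V5 + 1 + 30

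**Results at scheduled days, last dispensing at Visit 5**

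| | Protocol days (56/84) | SAP days (60/90) |
|---|---|---|
| Imputed last dose | 57 | 61 |
| Exposure, imputed vs true | 57 vs about 84 | 61 vs about 90 |
| Last usable diary day | 64 | 68 |
| Week 12 diary days | 81-83, none kept | 87-89, none kept |
| Window end, imputed vs true | 87 vs about 114 | 91 vs about 120 |

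On protocol days exposure is 57/84 = 0.68 of the true value, 32% too short, and the subject moves from the category of 84 days or more to that of 56 to 83 days. The Week 8 diary (Days 53-55) survives the Day 64 cut-off and becomes the end-of-treatment value.

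**All in-window visit days.** The closest protocol case is Visit 5 on Day 63 and Visit 6 on Day 77. The cut-off is 63 + 8 = 71 and the first diary day is 74, 3 days too late. The closest SAP case is Days 67 and 83: cut-off 75, first diary day 80, 5 days too late. So no Week 12 diary day survives in any in-window combination. Imputed exposure is 50-64 days (protocol) or 54-68 days (SAP).

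**Per protocol set.** With Visit 5 on Day 49, 50 or 51, imputed exposure is 50, 51 or 52 days, below 53, and criterion 1 is met. On SAP days the minimum is 54, so it is not.

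**Adverse events.** At scheduled protocol days the window closes on Day 87, after the true last dose at about Day 84. The events lost are post-treatment ones, from Day 88 to the Day 112 call. On-treatment events are lost only if the true last dose falls after V5 + 31, that is, more than 31 days after Visit 5. With Visit 5 on Day 49 the window closes on Day 80, before a Day 84 visit. With Visit 5 on Day 56, Visit 6 would have to be on Day 88 or later.

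**If drug is dispensed at Visit 6.** The imputed last dose becomes Day 85 or 91, the diary cut-off Day 92 or 98, and all three diary days are kept.

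**Run-in.** Neither schedule dispenses at Screening, so the start rule falls through to Screening plus one day: -28 + 1 = Day -27, against a first run-in dose at about Day -14. That is about 13 days early.

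**The case against.** The strongest reply is that the diary loss is inferred. Only SAP 6.3.1 expressly uses imputed dosing dates, and SAP 7.10.1 describes their purpose as classifying medication as before or during double-blind treatment. Neither the diary rule nor the adverse event rule mentions imputation, and the lead definition of a treatment-emergent event in SAP 6.2 has no end date. This stands as a qualification. But 7.10.1.1 defines the last dose date and makes no exception, so a programmer would naturally use the one derived date throughout.

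Second, the rule seldom fires. It needs a missing month or year and a tablet discrepancy or missing count, and completers have drug accountability at Visit 6. The likelier case is a subject lost after dispensing, who has no Week 12 diary to lose and for whom dispensing plus one day is a defensible convention. A reader might infer that the rule is wrong whenever it fires; the documents do not support that.

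Third, SAP Table 1 marks dispensing at Visit 6, under which the harm disappears. That stands: the result depends on which schedule governs.

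Fourth, protocol 2.2.2 says the Week 4 effect in the earlier programme was already close to its maximum, so using Week 8 values for a few subjects may change little. Nothing in the documents shows otherwise.

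A reader might also infer that on-treatment adverse events are generally dropped. At scheduled timing they are not. Finally, numbering randomization as Visit 2 is a label slip beside the correct visit name, low in its list, with little effect.

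**Conclusion.** The point holds in conditional form. For a completer who meets the trigger under the protocol schedule, exposure is understated by about 27 days (84 - 57); this rests on explicit text. If the imputed date also serves the diary and adverse event rules, the whole Week 12 diary is lost, end of treatment falls back to Week 8 for both co-primary endpoints, and the treatment-emergent window closes about 27 days early. That costs post-treatment events from Day 88, and on-treatment events only when Visit 6 falls unusually long after Visit 5, for example an early Visit 5 with an on-time or late Visit 6. An early Visit 5 (Days 49-51) also meets PPS criterion 1.

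The assumptions are that Visit 5 is the last dispensing and that the subject completed treatment. A gap in the day alone goes to month end and is outside the point. The documents do not give the number of affected subjects, so no effect on the co-primary results can be calculated; it is probably small. The rule is worth correcting because it can replace observed data with older data when better dates are already collected. It is not evidence that the primary result is at risk.

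**What to change.** 1. In SAP 7.10.1.1, put ahead of the dispense date: the last medication intake recorded in the e-diary, then the last drug-return or accountability date or the end-of-treatment or discontinuation visit date. Allow none of these to run beyond what the tablets dispensed could cover. Keep dispense date plus one day only when none of them exists.
2. State in SAP 7.10.3.1 that an observed Week 12 diary is not excluded on the strength of an imputed last dose date, and say in SAP 6.2 which date closes the treatment-emergent window.
3. Reconcile the dispensing visits in SAP Table 1 with those in protocol Table 1.
4. In the run-in rules, replace dispensing at Screening with Visit 2 and number the randomization visit as Visit 3, in line with the SAP's own Table 1. Point SAP 6.3.1 to 7.10.1.1.

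With the revised order, a completer on protocol days has a last dose at about Day 84, a diary cut-off of Day 91 with all three diary days kept, exposure of 84 days and a window to Day 114. The cost is SAP wording and derivation code. The e-diary intake times, drug accountability and visit dates are already collected.
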